7.6. Sensitivity analysis

We will investigate the influence of missing data using sensitivity analyses that make different assumptions, such as "best" and "worst" case scenarios, as well as using multiple imputation by chained equation (mice) to impute missing data.

7.6.1 Overlap

A small number of patients (≤15) who are involved in the STAR trial may also be involved in similar interventional trials and thus may influence one or both trials results. We will record which patients are involved in both trials and a sensitivity analysis will be performed as a repeat of the primary analysis on patients who are only involved in STAR.

Patient burden is an issue which will be addressed in recruitment of the STAR trial. To avoid increased withdrawal among patients involved in both trials the requirements of the patient, in terms of questionnaires and follow-up for the STAR trial, will be made very clear. Patients will also be informed that the two trials are separate trials and declining participation in one will not affect participation in the other.

Sensitivity analysis results for the primary outcomes to deal with any potential overlap will be presented in **Table 32** and **Table 33**.

7.6.2 Per protocol and CACE analysis

We propose to carry out per protocol analyses. It will only compare individuals who remained in their allocated treatment group throughout the trial. Since this analysis is likely to be biased, we will also use the Complier Average Causal Effect (CACE) approach if the quantity of compliant patients (those patients in the intervention group who attend their initial assessment clinic and those in the control arm who continue with usual care) satisfies the rule which we state in section *6.4. Compliance.* This provides an unbiased estimate for the treatment effect for those who have complied with the treatment group allocation. Compliers would be defined as a patient who attends the assessment clinic (intervention). This approach would be justified if the characteristics of those who adhered to the comparator treatment differed from those that adhered to the intervention. Results from these analyses will be presented as in **Table 32** - **Table 44**. If there is differential adherence in the two arms we will also investigate structural mean approaches as described by Fischer et al (Fischer, Goetghebeur, Vrijens, & White, 2011) and, separately, use extensions of CACE as described by White et al (White, Kalaitzaki, & Thompson, 2011).

7.6.3 Analysis accounting for time delay in assessment clinic

Since some of the patients had their assessment clinic more than 3 months after their TKR surgery we will repeat the primary analysis but restrict it to those patients who had their assessment clinic within three months of their TKR surgery as stated in the protocol.

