4. GENERAL ANALYSIS CONSIDERATIONS

4.1. Analysis populations

The primary analysis of the data will be on a complete case basis, in accordance as far as possible with the intention to treat (ITT) principle whereby we analyse as randomised, disregarding protocol deviations or non-compliance. Sensitivity analyses will utilise imputation methods to handle missing data to ascertain whether their exclusion in the primary analysis has had any effect within an ITT paradigm. In addition, a crude per protocol analysis will be performed using those patients who adhered with the intervention sufficiently. Adherence to the intervention, for a patient in the intervention arm, is defined as the patient attending their assessment clinic appointment and for patients in the control arm, adherence cannot be measured as they adhere by using usual care. We assume that all patients in the control arm have adhered to the intervention allocation. This per protocol analysis will address the same points as the comparison based on groups as allocated (hereafter referred to as 'the ITT analysis') just using a different population. Since these results are likely to be biased, we will also use the Complier Average Causal Effect (CACE) approach to adjust for any selection effects in terms of adherence.

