6. ASSESSMENT OF TRIAL QUALITY

6.1. Eligibility checks

The number of patients who were assessed and were not eligible for participation in the trial will be described in **Table 4**. The STAR trial eligibility criteria have been designed to minimise patient risk. The reason for exclusion will also be recorded in **Table 4**.

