6.4. Compliance

A complier to treatment is defined as a patient in the intervention arm who attends the assessment clinic or a patient in the control arm who complies with usual care (all patients in the control arm). Since non-compliance numbers are likely to be low, we set a rule to decide if we will use CACE analysis. If compliance is close to 100% then ITT analysis will be very similar to CACE analysis and so the latter will not be (additionally) informative.

If compliance is greater or equal to 95%, we will rule out the need for using CACE analysis. For compliance between 85% and 95% we will consider carrying out CACE analysis depending on the extent and pattern of adherence. For compliance below 85% we will use CACE analysis. Compliance rate will be recorded in **Figure 2**.

Compliance is recorded in **Table 46** by site and in total.

Descriptions of the number of follow up calls that the intervention group patients receive will be presented by site and in total. The time to first follow-up call will also be summarised by site and in total. These summaries can be found in **Table 47.**

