7.3. Primary analysis

The primary and main secondary analyses will be conducted using the ITT principle (that is, comparisons of groups as allocated) using the appropriate regression model. Assumptions for each regression will be checked to make sure the correct method of analysis is being used.

Each of the co-primary outcome measures, BPI Severity and BPI Interference scales, will be analysed to compare treatment groups using linear regression. The models will be adjusted for trial centre as a fixed effect and baseline BPI pain scores. Estimates will be calculated of the effect that intervention has on each of the BPI scores compared with usual care. Primary analysis will be adjusted for variables which are imbalanced at baseline to see if this makes a marked difference to the unadjusted primary analysis.

Results from the primary analysis will be presented in **Table 14**.

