7.4. Secondary analyses

7.4.1 Adjusting for "time to assessment clinic"

The primary analysis will be repeated including a variable which adjusts for the time between randomisation and assessment clinic. This variable will be included as a covariate in the model. The results for this can be found in **Table 15**.

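### The clinic-delay sensitivity analysis in SAP 7.6.3 sets no rule for controls and, on its likely reading, selects only the intervention arm on an event after randomisation

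*SAP*

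**What the plan says.** Section 7.6.3 notes that some clinics took place more than three months after surgery. It repeats the primary analysis on a reduced set: it will "restrict it to those patients who had their assessment clinic within three months of their TKR surgery", a timing it attributes to the protocol. The section does not say how usual-care patients enter, carries no caution about interpretation and names no results table.

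The analysis being repeated is the one in section 7.3, in which each BPI scale "will be analysed to compare treatment groups using linear regression", with adjustment for centre and baseline BPI.

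Three other places bear on who has a clinic and when:

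- Section 4.1: "Adherence to the intervention, for a patient in the intervention arm, is defined as the patient attending their assessment clinic appointment", whereas "for patients in the control arm, adherence cannot be measured as they adhere by using usual care".
- Section 6.4: a complier is "a patient in the intervention arm who attends the assessment clinic or a patient in the control arm who complies with usual care", and every control counts as one. Table 46 counts attendance only among those randomised to intervention.
- Section 7.4.1 uses a covariate that "adjusts for the time between randomisation and assessment clinic", so the clinic comes after randomisation.

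Sections 4.1 and 7.6.2 describe the per protocol analysis as likely to be biased and pair it with CACE, subject to the compliance thresholds in section 6.4.

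**The concern.** The rule in 7.6.3 depends on a variable that exists in one arm only. A between-arm contrast cannot be restricted on such a variable without losing either the comparator or the protection of randomisation.

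The analysis is there to show whether late delivery diluted the effect. Patients seen promptly may differ from those seen late or never, for example in health, mobility or distance from the site. If so, a larger difference in the restricted set could come from delivery on time, from who was left in, or from both, and the planned output cannot tell these apart. A reader could then credit prompt delivery with a benefit, or blame it for a harm, that selection produced.

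**Working it through.** **1. Reproduce the SAP's own figures (section 3.7).** Inputs: 380 randomised, 25% loss, 2:1 allocation, SD about 2, two-sided 5%.

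- Analysed: 380 × 0.75 = 285, that is 190 intervention and 95 control.
- Standard error of the difference: 2 × √(1/95 + 1/190) = 0.251 points.
- Power at 0.7 points (0.35 SD): Φ(0.7/0.251 − 1.96) = 79.5%. At 0.8 points (0.40 SD): 88.9%.

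The stated 80% to 90% is reproduced.

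**2. Literal reading.** Keep patients with a clinic within three months. By sections 4.1 and 6.4 and Table 46, no control has a trial clinic attendance to date. Everyone retained is in the intervention arm, so the group indicator is constant and collinear with the intercept. No difference in means can be estimated.

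**3. Likely reading: all controls kept.** Let s be the share of the intervention arm excluded (late attenders plus non-attenders). Let m_E and m_R be the mean outcomes of excluded and retained intervention patients after adjustment for centre and baseline BPI, and m_C the control mean. The whole intervention arm has mean

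s·m_E + (1 − s)·m_R.

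Therefore

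m_R − m_C = (whole-arm difference) − s × (m_E − m_R).

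The restricted estimate departs from the ITT difference by s times the residual gap. This identity holds whatever caused the gap, so dilution by delay and selection of better-placed patients enter it in the same way.

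**4. Size when the true effect is zero.** The SAP gives neither s nor the gap; both are assumed here, with excluded patients doing worse. BPI scores run from best to worst, so a negative difference favours the intervention.

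| Share excluded | Residual gap 0.5 | Residual gap 1.0 |
|---|---|---|
| 20% | −0.10 | −0.20 |
| 30% | −0.15 | −0.30 |
| 50% | −0.25 | −0.50 |

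If excluded patients did better, the signs reverse. If the gap is zero, the bias is zero.

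**5. Against the noise.** With 20% excluded (152 retained), the standard error is 2 × √(1/95 + 1/152) = 0.262. A bias of 0.10 is 0.38 standard errors, and a nominal 5% test would reject about 6.7% of the time. With 50% excluded (95 retained), the standard error is 0.290. A bias of 0.50 is 1.72 standard errors, and the test would reject about 41% of the time.

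**6. Cross-check with another model.** Suppose delay is continuous, has correlation r with the residual outcome (SD 2), and the fastest fraction f is kept. The bias is 2 × r × φ(z_f)/f. For f of 0.75 or 0.50 and r from 0.1 to 0.3 this gives 0.08 to 0.48 points, much the same range. Again r and f are assumed.

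**7. Loss of precision.** Even without bias, keeping 75% of the intervention arm gives power of 75.3% and 85.5% at 0.35 and 0.40 SD. Keeping 50% gives 67.4% and 78.7%.

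**The case against.** The strongest reply is that 7.6.3 is easily understood. It repeats a comparison of two arms, and sections 4.1 and 6.4 treat every control as compliant, so an analyst would keep all controls and drop late intervention patients. This stands as a reading of intent. A reader might infer that the plan really discards its comparator; the documents do not support that as the likely meaning, although it is what the sentence says. The reply leaves the second problem untouched, because the intended version is the one that selects a single arm.

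Second, centre is a fixed effect and baseline BPI a covariate, so differences between centres in clinic delay are adjusted for, and differences in health partly so. This also stands. Only the residual gap matters, and if delay came from clinic capacity or scheduling the bias could be negligible.

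Third, the reference to the protocol might bring in a rule for controls. The protocol is not at hand, so this cannot be excluded. As the sentence is built, however, the reference attaches to the three-month timing, and the SAP itself defines the analysis set here.

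Fourth, this is one sensitivity analysis. That is true, and it limits the severity.

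**Conclusion.** The point holds as a defect in one sensitivity analysis. As worded, 7.6.3 either cannot be estimated or, more plausibly, compares selected intervention patients with unselected controls. The SAP recognises this kind of selection as a source of bias for the per protocol set. Here it selects more strictly (attended and on time) and says nothing.

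The size is unknown. The range of 0.10 to 0.50 BPI points rests on assumed exclusions of 20% to 50% and assumed residual gaps of 0.5 to 1 point; it could be near zero, and the direction is not established. Two stronger conclusions might be inferred and are not supported. One is that the restricted result is known to favour the intervention: the SAP gives no data on who was seen late. The other is that the main result is compromised: the primary analysis compares groups as randomised and does not use clinic timing.

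Section 7.4.1 shares the root problem, since time to clinic is undefined for controls. The two should be settled together and counted once.

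**What to change.** Replace the one-arm restriction by one of the following.

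1. **Preferred: CACE or instrumental-variable analysis with timely attendance as compliance.** Keep all randomised patients with outcome data as in the primary analysis, use allocation as the instrument, and define compliance as attending the clinic within the SAP's own three-month window. State what is assumed about late attendance. Let p be the share attending on time and l the share attending late. Assume that allocation does not affect non-attenders. If late attendance has no effect, the prompt-attender effect is ITT/p. If it works as well as prompt attendance, the effect is ITT/(p + l). Reporting both brackets the answer when the late effect lies between zero and the prompt effect. Say also whether the thresholds in 6.4, which are written for any attendance, govern this analysis.

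2. **Alternative: restrict both arms alike.** Use a cut-off on time from surgery to randomisation, fixed before the data are examined by arm. This keeps a randomised comparison but answers a different question (randomised early enough, not seen on time), and the confidence interval will be wider.

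An interaction of arm with time from surgery to randomisation may be added as a separate analysis. It estimates something other than the subset effect and should not be presented as its equivalent.

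If the one-arm restriction is still reported, state that all controls are retained, label it a non-randomised comparison, give the numbers of late attenders and non-attenders removed, and assign it a results table.

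The cost is a paragraph of SAP wording and an entry in Table 51. Option 1 needs surgery and clinic dates for the intervention arm and methods the SAP already plans to use. Option 2 needs surgery and randomisation dates in both arms.

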7.6.4 Repeated measures analysis

A repeated measures analysis will be performed using a multi-level mixed effects linear regression to model each of the BPI subscales (measured at 6 months and 12 months) on the baseline measure of the outcome, stratification variables and any variables which show imbalance at baseline. The repeated measures model will also include an interaction between the intervention allocation and the time point. The p-value of the interaction term will be the focus of analysis. This analysis will account for clustering within patient using a random effect. The analysis will include those patients who have at least one non-missing outcome over the two time-points. The results of this analysis will be presented in **Table 45**.

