3.6. Randomisation procedures

After patients have provided written, informed consent to participate and have completed and returned a baseline questionnaire, they will be randomly allocated to the STAR pathway or usual care. Randomisation will occur as soon as possible after the baseline questionnaire is received by the research team. Randomisation with allocation concealment will be conducted remotely via the Bristol Randomised Trials Collaboration using a web-based randomisation system. Randomisation will take place on a 2:1 basis to ensure that the intervention service is running at sufficient capacity to enable a pragmatic assessment of its effectiveness and, particularly, cost-effectiveness. If the intervention is operating to a sufficient degree of capacity per-protocol and CACE analyses will be more reliable and have higher power. To ensure reasonable balance between the two treatment groups, allocation will be minimised by pain in the replaced knee (assessed with both the Brief Pain Inventory Severity and the Brief Pain Inventory Interference Scales – these scores are both categorised using tertiles of STAR PACE data for these scores) and stratified by orthopaedic centre. Randomisation will be performed by a member of the research team at the co-ordinating centre and the local researcher at each site will then inform participants of the result.

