4.3 Procedures for missing data

In all tables missing data will be indicated by footnotes. If the amount of missing data differs substantially between treatment groups potential reasons will be explored. Sensitivity

analyses will be conducted (including the use of multiple imputation by chained equations (mice) methods) to examine the influence of missing data on the key trial findings. When using mice, 25 datasets will be generated and 10 switching procedures undertaken. The imputation model will include all variables predictive of missingness, together with all of the variables included in the main substantive model. Comparisons of results from ITT analyses of complete cases with ITT analyses where missing data were imputed will be presented in **Table 17 - Table 29**.

The model used for imputation will include a baseline measure of the outcome, any other observations of the outcome at different follow-up times, randomisation group, age/gender, centre and any other restriction variables for the randomisation (i.e. stratification/minimisation), we will consider also including any other variables that are either strongly associated with missingness or likely to have some prognostic value. This list will be finalised before conducting the mice analyses.

In the event of missing data, we will follow guidelines where applicable and use mice to impute scores if the missingness exceeds the guidelines.

BPI (severity and interference): The first four items of section A must be complete to calculate the score for the severity scale. Four of the last seven items of section A of the questionnaire must be complete to calculate the interference scale by averaging complete items.

OKS: If 1 or 2 questions are missing, then the mean value can be used to fill the gaps.

PainDETECT: If any of the first seven items of section C are missing impute with the mean of the complete items in the first seven items. If question 8 of section C is missing do not add or subtract anything from the score (ie. Treat the value of that item as zero). If question 9 is missing, assume the response is no, thus, treat the value of the item as zero.

DN-4: No score can be calculated if more than 4 items are missing. The score is a proportion of "Yes" responses.

Short form-12: The short form-12 requires 50% of items to be completed.

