7.4.2 Secondary outcomes

The secondary outcomes will be analysed using appropriate regression models in a similar manner to the primary analysis. The models will adjust for trial centre, baseline BPI pain score and also the baseline scores of the outcome for which it is modelling. A summary of the primary and secondary outcomes can be seen in **Table 13.** Further adjustment for any observed baseline imbalance will only be made for secondary outcomes in the unlikely event that such adjustment had a material effect on the results for the primary outcomes, or if there is a particular cause for concern as a consequence of a known strong relationship between a specific outcome and an individual variable demonstrating (chance) imbalance at baseline.

Results from the secondary analysis will be presented in Table 16.

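### Read literally, the secondary and repeated-measures models each leave out one of the two BPI scales used in the minimisation; one explicit covariate list would settle it at almost no cost

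*SAP*

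**What the plan says.** SAP 3.6 uses two restriction devices. Allocation is minimised on pain in the replaced knee, "assessed with both the Brief Pain Inventory Severity and the Brief Pain Inventory Interference Scales", with both scores cut at tertiles, and it is "stratified by orthopaedic centre". Section 4.3 keeps the two terms apart: the imputation model takes "any other restriction variables for the randomisation (i.e. stratification/minimisation", so both kinds are named where both are meant.

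The analysis sections then give three covariate sets:

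- **7.3, primary:** "The models will be adjusted for trial centre as a fixed effect and baseline BPI pain scores".
- **7.4.2, secondary:** "The models will adjust for trial centre, baseline BPI pain score and also the baseline scores of the outcome for which it is modelling". The BPI score is singular and the scale is not named.
- **7.6.4, repeated measures:** the model is fitted "on the baseline measure of the outcome, stratification variables and any variables which show imbalance at baseline". The same section adds that "The p-value of the interaction term will be the focus of analysis".

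The table shells do not settle the matter. The adjustment footnotes to Tables 14 to 44 name centre and baseline OKS and no BPI score. The footnote to Table 45, the repeated-measures table, is blank.

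**The concern.** A model for a trial with restricted randomisation should include the factors that restricted it. If allocation is balanced on a prognostic factor and the model omits it, the reported standard error takes no credit for the balance. Intervals are then wider than they need be and tests are mildly conservative.

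Taken at its word, 7.6.4 fits Severity without baseline Interference and Interference without baseline Severity. Its clause on baseline imbalance would not normally bring the missing scale back, because minimisation exists to prevent that imbalance. Section 7.4.2 could be fitted with Severity, with Interference or with both. Section 1 of the SAP says that another analyst should be able to run the analysis from the document. Here two analysts could fit different models to every secondary outcome, and the choice would be made with the data in hand.

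**Working it through.** **1. The plan's own figure.** Section 3.7 gives 285 analysed at 2:1, hence 190 and 95. The unadjusted standard error, in SD units, is √(1/190 + 1/95) = 0.1257.

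- At 0.35 SD: 0.35/0.1257 − 1.96 = 0.825, power 79.5%.
- At 0.40 SD: 0.40/0.1257 − 1.96 = 1.223, power 88.9%.

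The stated 80% to 90% is reproduced.

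**2. Precision lost by omitting the other BPI scale.** Let r be the correlation between the two baseline scales, a the correlation of the outcome with its own baseline, and b its correlation with the other scale. Then

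partial R² = (b − a·r)² / [(1 − a²)(1 − r²)], and SE inflation = 1/√(1 − partial R²).

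The SAP gives none of these correlations, so all are assumptions:

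| r | a | b | partial R² | SE inflation |
|---|---|---|---|---|
| 0.5 | 0.5 | 0.3 | 0.004 | 1.002 |
| 0.5 | 0.5 | 0.4 | 0.040 | 1.021 |
| 0.5 | 0.5 | 0.5 | 0.111 | 1.061 |
| 0.5 | 0.6 | 0.5 | 0.083 | 1.044 |
| 0.7 | 0.5 | 0.3 | 0.007 | 1.003 |
| 0.7 | 0.5 | 0.4 | 0.007 | 1.003 |
| 0.7 | 0.5 | 0.5 | 0.059 | 1.031 |
| 0.7 | 0.6 | 0.5 | 0.020 | 1.010 |
| 0.8 | 0.5 | 0.3 | 0.037 | 1.019 |
| 0.8 | 0.5 | 0.4 | 0.000 | 1.000 |
| 0.8 | 0.5 | 0.5 | 0.037 | 1.019 |
| 0.8 | 0.6 | 0.5 | 0.002 | 1.001 |

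Ten of the twelve are at about 3% or below. With a = 0.5, power at 0.35 SD is 89.5% with own baseline only and 89.5% to 92.7% with both scales. The grid is not a ceiling. If the other scale predicted the outcome better than its own baseline did (r = 0.5, a = 0.5, b = 0.55), partial R² would be 0.09/0.5625 = 0.16 and the inflation 1.091.

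**3. Is the reported standard error too large for the true variability?** This was simulated with 1,500 trials per scenario: 285 patients, four centres, 2:1 minimisation on tertiles of both scales within centre, and no treatment effect. The model had centre and own baseline only.

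| r; coefficients own, other | mean model SE | empirical SD | ratio | type I error | type I error, both scales |
|---|---|---|---|---|---|
| 0.7; 0.40, 0.15 | 0.1082 | 0.1074 | 1.007 | 0.044 | 0.046 |
| 0.7; 0.35, 0.30 | 0.1040 | 0.1051 | 0.990 | 0.053 | 0.059 |
| 0.5; 0.40, 0.30 | 0.1045 | 0.1013 | 1.032 | 0.041 | 0.046 |

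Monte Carlo error is about 0.006 on the type I error and 1/√3000 = 1.8% on the SD. The overstatement lies between none and about 3%.

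**4. The quantity that 7.6.4 targets.** With complete data, allocation by time is the arm difference in change from 6 to 12 months. In the same simulations its type I error was 0.049 to 0.052, and the model SE matched the empirical SD (for example 0.0961 against 0.0956). Forty random-intercept fits (320 patients, simple 2:1 randomisation, 12% missing per visit, r = 0.7, coefficients 0.35 and 0.30) gave:

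| term | SE, own baseline only | SE, both scales |
|---|---|---|
| arm difference at 6 months | 0.1041 | 0.1010 |
| allocation by time | 0.0949 | 0.0948 |

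The first ratio is 0.1041/0.1010 = 1.031; the second is 1.001.

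**The case against.** The strongest reply is that the omission is inferred. Section 7.6.4 may use the word stratification loosely for every restriction factor. Section 7.4.2 says that the secondary models follow the primary one, whose BPI term is plural, so its singular may be a slip. That is fair: the SAP nowhere states an exclusion, and a reader who inferred a deliberate one would go too far. The objection makes the point one of ambiguity but does not remove it, because 3.6 and 4.3 use the two terms distinctly and the Table 45 footnote is blank.

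A reader might also infer that the main result of the repeated-measures analysis has an inflated standard error. It does not. The focal term is a within-patient contrast, and a baseline main effect hardly touches it. The small loss applies to a between-arm difference, which Table 45 has columns to report, and to the secondary models.

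Nor is it supportable to say that a discrepancy with the primary result could not be attributed because of this one covariate. Section 7.6.4 already differs by design in time points, model, patients included and focal parameter, so aligning the covariate would not make the two directly comparable.

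It also stands that each repeated-measures model keeps centre and one minimised scale, which is presumably correlated with the missing one, and that any error is on the conservative side.

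**Conclusion.** The covariate sets are inconsistent, and on a literal reading the secondary and repeated-measures models each lack one minimisation factor. For between-arm estimates the cost is a standard error about 0% to 6% larger, usually 3% or less, in the conservative direction. The interaction in 7.6.4 is essentially unaffected. The primary analysis is unaffected if the plural in 7.3 means both scales. That sentence covers two models, so it could also mean each model's own baseline; in that case the same small loss would apply there.

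The sizes rest on assumed correlations and on linear models for a BPI outcome. The secondary models, which already hold their own baseline and one BPI score, were not simulated separately, and the figures do not carry over to the logistic model for the body map. Nothing here biases a result. This is a free improvement in precision and a needed clarification; it does not show that the planned analyses are invalid.

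**What to change.** In 7.3, 7.4.2 and 7.6.4, state one covariate set for every between-arm model: trial centre, continuous baseline BPI Severity, continuous baseline BPI Interference, and the outcome's own baseline where it is not one of these. In 7.6.4, replace *stratification variables* with *stratification and minimisation variables (centre and both baseline BPI scores)*. Bring the footnotes to Tables 14 to 44 into line, since they now cite baseline OKS, and complete the footnote to Table 45. The OKS footnotes are the more visible conflict with 7.3 and would survive if only the text sections were edited.

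The cost is wording and one degree of freedom per model. Both scores are in hand before randomisation, because allocation uses them.
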